The PI and co-investigators will review any adverse events after each experiment to determine severity (serious or non-serious), expectedness (expected or unexpected) and relatedness (related, possibly related or unrelated). The study investigator will assess the relationship of any adverse event to be related or unrelated by determining if there is a reasonable possibility that the adverse event may have been caused by the study intervention.

To ensure consistency of adverse event causality assessments, investigators should apply the following general guideline when determining whether an adverse event is related:

Related: There is a plausible temporal relationship between the onset of the adverse event and the study intervention, and the adverse event cannot be readily explained by the participant's clinical state, intercurrent illness, or concomitant therapies; and/or the adverse event follows a known pattern of response to the study intervention; and/or the adverse event abates or resolves upon discontinuation of the study intervention or dose reduction and, if applicable, reappears upon re-challenge.

Possibly Related: Possibly related to the research means there is a reasonable possibility that the adverse event, incident, experience or outcome may have been caused by the procedures involved in the research (modified from the definition of associated with use of the drug in FDA regulations at 21 CFR 312.32(a)). Reasonable possibility means that the event is more likely than not related to participation in the research or, in other words, there is a >50% likelihood that the event is related to the research procedures

Not Related: Evidence exists that the adverse event has an etiology other than the study intervention (e.g., preexisting medical condition, underlying disease, intercurrent illness, or concomitant medication); and/or the adverse event has no plausible temporal relationship to study intervention.

Serious adverse event means any event temporally associated with the subject's participation in research that meets any of the following criteria:

- results in death
- is life threatening (places the subject at immediate risk of death from the event as it occurred)
- requires inpatient hospitalization or prolongation of existing hospitalization;
- results in a persistent or significant disability/incapacity
- results in a congenital anomaly/birth defect

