- any other adverse event that, based upon appropriate medical judgment, may jeopardize the subject's health and may require medical or surgical intervention to prevent one of the outcomes listed above (examples of such events include allergic bronchospasm requiring intensive treatment in the emergency room or at home, blood dyscrasias or convulsions that do not result in inpatient hospitalization, or the development of drug dependency or drug abuse).

Reporting Guidelines

Any serious adverse events or unexpected but related or possibly related adverse events will be communicated to the PI as soon as possible and within 48 hours of the time they are detected. Adverse

events will be reported promptly to the Partner's IRB and to the BU IRB, the DSMB, Beta Bionics and Zealand Pharma. Collaborator [name] is the sponsor of the Investigational Device Exception (IDE) for the bionic pancreas to be used in this trial. Zealand Pharma is the sponsor for the Investigational New Drug (IND) application for dasiglucagon to be used in this trial. Reports of adverse events will be made to the FDA in compliance with the terms of IDE and IND.

XI. Subject Compensation

Financial compensation will be provided to all subjects who complete the screening visit. Subjects will be paid \$25 for completing the screening visit whether or not they are eligible to participate in the study.

Study participants will be compensated \$50 for completing each study visit. Thus, the total compensation for a subject who completed screening and all five study visits would be \$275.

Parking expenses will be paid for up to \$30 per subject for each visit. Subjects who are unable to complete the study or chose to stop participation will receive prorated compensation for the portion of the study visits that they complete.

Designated contacts will be compensated \$25 for completing the screening visit, \$25 for completing the study, and \$25 for completing their questionnaires. The total compensation available for designated contacts is \$75.

XII. References

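### Possibly Related is set at more than 50% likelihood, so some plausible adverse events fit no causality category, and non-serious unexpected ones miss the 48-hour route to the principal investigator

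*Combined protocol and SAP*

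**What the plan says.** All the causality wording is in section X.c, under Definitions.

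- The reviewing investigators grade each event on three levels: "relatedness (related, possibly related or unrelated".
- The next sentence has two levels: "The study investigator will assess the relationship of any adverse event to be related or unrelated by determining if there is a reasonable possibility" of causation by the study intervention.
- Possibly Related is then defined by the same term, reasonable possibility, which is given a threshold: "Reasonable possibility means that the event is more likely than not related to participation in the research". The sentence continues by restating this as a figure: "there is a >50% likelihood that the event is related to the research procedures".
- Related has no probability threshold. It is met by plausible timing without a ready alternative explanation, "and/or the adverse event follows a known pattern of response to the study intervention", and/or by improvement when the intervention is stopped or reduced.
- Not Related needs a positive finding: "Evidence exists that the adverse event has an etiology other than the study intervention", and/or "the adverse event has no plausible temporal relationship to study intervention".

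Under Reporting Guidelines, still in X.c, the label has a consequence: "Any serious adverse events or unexpected but related or possibly related adverse events will be communicated to the PI", with a limit of 48 hours from detection.

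**The concern.** The middle category has a stricter numerical bar than the category above it. Its name suggests that a link cannot be ruled out, but its definition requires that a link be probable. The category below it is not a residual category either, because it requires evidence against a link. Events between the two have no defined label, although the stated purpose of the definitions is consistent causality assessment.

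The matter counts because safety is part of the study's objective (section II) and section VIII accepts that dasiglucagon may carry unknown risks. The only results with dasiglucagon in the device that the protocol reports are from 20 adults treated for up to 8 hours (section I.e); here the bihormonal arm lasts 7 days. A new effect has no known response pattern, so that route to Related is closed to it. With so little prior exposure, an investigator may also be slow to rate a link as more likely than not. The middle category is where such an event should be caught.

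**Working it through.** No arithmetic applies, since the 50% figure is a definition. The check is whether the categories cover every event, and where the label changes what is reported.

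**Step 1: coverage of the three-level scale.** Take a new symptom not named in section VIII. Its timing is plausible. An intercurrent illness could readily explain it, but there is no evidence that it did. There is no known pattern and no information yet from stopping or reducing the intervention. Suppose, for illustration, that the investigator puts the likelihood of a link at 30%.

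| Category in X.c | Requirement | Met? |
|---|---|---|
| Related | Plausible timing and no ready alternative explanation | No: an alternative is at hand |
| Related | Known response pattern | No |
| Related | Improves on stopping or reduction | No information |
| Possibly Related | Likelihood above 50% | No: 30% |
| Not Related | Evidence of another cause | No: only a candidate cause |
| Not Related | No plausible timing | No: timing is plausible |

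The event has no category. The same holds for any likelihood up to and including 50%, other facts unchanged.

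**Step 2: the two-level sentence.** It decides between related and unrelated by reasonable possibility, the term that the section sets above 50%. At 30% the event is unrelated. The section thus gives one event two answers: no category, or unrelated.

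**Step 3: effect on the 48-hour route.** For an event in the gap:

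| | Expected | Unexpected |
|---|---|---|
| Serious | Sent within 48 hours whatever the causality; threshold has no effect | Sent within 48 hours whatever the causality; threshold has no effect |
| Non-serious | Not on the route under any label; threshold has no effect | On the route only if related or possibly related; **lost** |

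One cell of four is affected, and within it only events at or below 50% that meet no Related criterion.

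**Step 4: what does not depend on the label.**

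- X.b: the Data and Safety Monitoring Board (DSMB) is told of all serious events.
- X.c: all adverse events are reviewed after each experiment.
- X.c: adverse events go promptly to the ethics boards, the DSMB and both companies, with no causality condition and no stated number of hours.
- VII.d.iv: the tables show treatment-emergent events by system organ class and preferred term, without a relatedness filter.

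**The case against.** The strongest reply is that little is lost. The single item at risk is a 48-hour message to the principal investigator, who reviews every event after each experiment in any case. The DSMB also reviews compiled safety data periodically, and nausea, vomiting and skin reactions are actively solicited. X.b sets a 72-hour DSMB report for serious and unexpected events; if that means serious events plus unexpected ones, rather than events that are both, non-serious unexpected events would reach the DSMB quickly too. X.b also mentions unanticipated adverse device events, which the protocol does not define. All this stands, and it limits the harm. It does not give the event a category or reconcile the two scales.

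A second reply is that the gap is small. Plausible timing with no ready alternative explanation is enough for Related, and an event that clears when an arm ends may qualify by improvement on stopping. That also stands, although information from stopping may not exist when the 48-hour decision is due.

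A reader might go further and infer one of the following, none of which the documents support:

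- *Every plausible event at or below 50% escapes expedited review.* Serious events do not, and the Related criteria capture some of the others.
- *The safety tables will understate harm.* They do not use relatedness.
- *Reports to the FDA will be incomplete.* The protocol says only that they follow the terms of the device and drug applications, so this cannot be settled either way.

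**Conclusion.** The defect is real and limited. Taken literally, X.c leaves a plausible event at or below 50% without a category when it meets no Related criterion, and calls it unrelated under the two-level sentence. The practical loss is the 48-hour communication of such events when they are non-serious and unexpected. Serious events, the review after each experiment and the safety tables are unaffected.

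The number of events cannot be stated, because the documents give no expected rate of unexpected non-serious events and no likelihood ratings. The conclusion assumes that investigators apply the definitions as written; in practice some would assign a label by judgement, and different investigators could then label the same event differently. It does not depend on which reading of the 72-hour DSMB rule is intended, since the route to the principal investigator is separate.

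This should be corrected because the rule bears on safety and the correction is cheap. It is not a flaw in the design or the analysis.

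**What to change.** In section X.c:

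1. Delete the sentence that equates reasonable possibility with more likely than not and with more than 50%.
2. Delete the two-level sentence and keep one three-level scale.
3. Limit Not Related to events with no plausible timing, or where evidence of another cause excludes a link to the device, drug or procedures. If this definition is left as it is, the wider Possibly Related category would overlap with it, and the gap would be replaced by a double classification.
4. Define Possibly Related as plausible timing where a link to the device, drug or procedures cannot be excluded, for events that do not meet Related.
5. State the order of application: Not Related first, then Related, with Possibly Related for what remains. Each event then falls in exactly one category.
6. Keep treating related and possibly related events alike for the 48-hour route, as the plan already does.

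The cost is protocol and case report form wording, and a few more events communicated to the principal investigator. No endpoint, sample size or planned table changes.
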